#### *Compliance to exercise*

**Aerobic exercise** 20 minutes per day, 3 days a week

Weekly maximum score = 3 (compliant 3 days/week)

Compliance is calculated weekly by dividing the actual weekly score by the maximum weekly score multiplied by 100.

$$\frac{\text{actual score}}{3} \times 100\%$$

Participants found to have compliance of <80% will be counseled. Compliance of <70% will be considered as non-compliant and any participant demonstrating non-compliance for two consecutive weeks will be withdrawn from the study.

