#### *Removal by Qualified Investigator*

Protocol 20BWHM:

A randomized, double-blind, placebo-controlled study to investigate the effects of a *Bifidobacterium breve* strain on fat loss in healthy adults

Participant discontinuation should be considered at the discretion of the qualified investigator. The circumstances of any discontinuation must be documented in detail in the participant file and final report. If possible, the evaluations planned for the end of treatment will be carried out at the time when the participant is withdrawn from the study.

Criteria for removal of participants from the study includes:

*Clinical reasons*

A participant may be withdrawn from the study if, in the opinion of the qualified investigator, it is not in the participant's best interest to continue. Any participant who experiences a serious adverse event (SAE) may be withdrawn from the trial at the discretion of the qualified investigator. A participant will also be withdrawn due to adverse events causing clinically significant illness or the need for prohibited medication(s) during the trial. Any female participant who becomes pregnant during the course of the trial will be withdrawn and will be followed up until giving birth.

*Protocol violation*

Any participant found to have entered this study in violation of the protocol will be discontinued from the study at the discretion of the qualified investigator. This will include any participant found to have been inappropriately enrolled (did not meet eligibility criteria). Participant non-compliance includes failure to show up for study visits, failure to take the investigational product as directed, or refusal to undergo study visit procedures. Participants who are found to be taking prohibited medications or supplements without the knowledge of the qualified investigator will also be withdrawn. Any major protocol deviations (i.e. those that increase the risk to participants and/or compromise the integrity of the study or its results) will result in participant discontinuation.

*Participapnt Replacement*

For all early withdrawals, a participant leaving the study prematurely or in the event of participant removal will NOT be replaced by another. It is understood by all concerned that an excessive rate of withdrawals can render the study un-interpretable, thus unnecessary withdrawal of participants should be avoided.

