### **11.2.2 Treatment and Follow-up of Laboratory Abnormalities**

In the event of participant-initiated withdrawal or clinically significant unexplained abnormal laboratory test values, the participant will be withdrawn from the treatment and will remain in the study and be required to attend all remaining study visits as part of a safety arm.

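### Protocol 10.12 withdraws randomized participants for short exercise weeks without keeping them to the week-12 DXA, the only scheduled post-baseline measurement of the primary endpoint

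*Protocol*

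**What the plan says.** Protocol 10.12 (Compliance to exercise) asks for 20 minutes of aerobic exercise on three days a week. The score is described as "Weekly maximum score = 3 (compliant 3 days/week", and compliance is the week's score divided by 3. Two cut-offs follow. The milder one is "Participants found to have compliance of <80% will be counseled". The stricter one is "Compliance of <70% will be considered as non-compliant and any participant demonstrating non-compliance for two consecutive weeks will be withdrawn from the study". The section does not say how a partly completed session is scored.

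Protocol 7.5 deals with removal in general terms: "Participant discontinuation should be considered at the discretion of the qualified investigator". It adds that too many withdrawals can spoil the study, "thus unnecessary withdrawal of participants should be avoided", and that withdrawn participants are not replaced. On data at exit it says: "If possible, the evaluations planned for the end of treatment will be carried out at the time when the participant is withdrawn".

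Protocol 11.2.2 has a stay-in-study clause, with a limited trigger: "In the event of participant-initiated withdrawal or clinically significant unexplained abnormal laboratory test values". Such a participant "will be withdrawn from the treatment and will remain in the study and be required to attend all remaining study visits", in what the section calls a safety arm.

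The schedule (1.3) and section 10.8 place DXA at weeks 0 and 12 only. The primary outcome is the 12-week DXA change. ITT (protocol 12.2, SAP 3) requires some post-randomization efficacy information, and the first visit after baseline is week 6.

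**The concern.** The rule acts after randomization and is worded as mandatory. It removes people from the study, not just from treatment, for a shortfall that may be slight. Nothing then secures their week-12 DXA. A participant who chooses to leave is asked to attend the remaining visits, while a willing participant removed over two missed sessions is not.

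At stake are primary-endpoint values from people who exercised almost as prescribed. Anyone withdrawn before week 6 without an exit evaluation could also fall outside ITT, since no post-randomization efficacy value would exist.

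The two cut-offs add to the difficulty. Different percentages suggest that a milder tier was intended, but on whole-day scoring no week can fall between them.

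**Working it through.** **1. The plan's own figure.** Inputs from protocol 12.1: difference 0.76%, SD 1.19%, two-sided 5%, 50 per arm, 20% attrition. Completers are 50 × (1 − 0.20) = 40 per arm. Two-sample t power at 40 per arm is 80.5% (80.3% for 0.79 kg with SD 1.24 kg). The stated 80% is reproduced. For reference, power is 88.5% at 50 per arm and 79.5% at 39.

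**2. The cut-offs.** Compliance = score/3 × 100, whole points:

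| Score | Compliance | Below 80% | Below 70% |
|---|---|---|---|
| 0 | 0% | yes | yes |
| 1 | 33.3% | yes | yes |
| 2 | 66.7% | yes | yes |
| 3 | 100% | no | no |

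Both cut-offs pick out the same weeks. Part-credit would change this (2.25/3 = 75% lies between them), but none is defined. Over 12 weeks there are 36 sessions. Missing one in each of two adjacent weeks leaves 34/36 = 94% and still meets the trigger.

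**3. How many might be withdrawn.** The documents give no adherence rate, no make-up rule and no fixed exercise days, so what follows is an assumed range. Let p be the chance of completing a session (independent sessions) and q the chance of a short week:

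- No make-up: q = 1 − p³.
- Half of missed sessions made up: the same, with p replaced by 1 − (1 − p)/2.
- One spare day: q = P(Bin(4, p) < 3).
- Two spare days: q = P(Bin(5, p) < 3).

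Let a be the probability of being still in the study after a full week, and b after exactly one short week. Each week a becomes (a + b)(1 − q) and b becomes (old a) × q. Starting from a = 1 and b = 0, the withdrawal probability after 12 weeks is 1 − a − b.

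Example: p = 0.95 with no make-up gives q = 1 − 0.857 = 0.143 and a withdrawal probability of 0.184.

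| Assumption | p = 0.97 | p = 0.95 | p = 0.90 |
|---|---|---|---|
| Two spare days | <0.001% | 0.002% | 0.08% |
| One spare day | 0.03% | 0.2% | 2.8% |
| Half made up | 2.1% | 5.4% | 18% |
| No make-up | 7.5% | 18% | 50% |

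Eleven of the 12 cells are below the planned 20%.

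**4. Power for 0.76%, counting withdrawn participants as lost.** With this rule as the only cause of loss, n = 50 × (1 − w), where w is the withdrawal probability. With no make-up, n is 46.2 / 40.8 / 24.8 per arm and power is 86 / 81 / 60%. Only that last cell of the 12 falls below 80%.

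If another 10% are lost for other reasons (assumed), n = 45 × (1 − w):

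| Assumption | p = 0.97 | p = 0.95 | p = 0.90 |
|---|---|---|---|
| Two spare days | 85% | 85% | 85% |
| One spare day | 85% | 85% | 84% |
| Half made up | 84% | 83% | 77% |
| No make-up | 82% | 77% | 55% |

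These figures ignore imputation, which the plan provides for missing efficacy values.

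**5. What would hold a withdrawn participant to week 12.** Section 7.5 offers an evaluation at the time of withdrawal, if feasible, and that could include a DXA. It would be taken early and is not the 12-week measurement. Section 11.2.2 requires continued attendance, but for two other causes. Section 10.12 is silent. No clause covers this case.

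**The case against.** The other side has several good points.

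- **Losses are probably small.** No exercise days are fixed, so a missed session can usually be moved. On the spare-day rows the loss is at most 2.8%. Participants must have complied during the run-in (9.4), and bi-weekly calls check exercise (9.3). This stands, and the high-loss cells should not be read as a forecast.
- **The sample size already budgets 10 losses per arm.** This stands. A reader might infer from the no-make-up row that the trial is underpowered, but the documents give no adherence rate that would support this.
- **The tiers still differ in effect.** Withdrawal needs two consecutive short weeks, so a single short week leads only to counselling. This stands. It would be too strong to say that counselling without withdrawal never happens. The emptiness of the band between the cut-offs also depends on whole-day scoring, which 10.12 does not state.
- **An exit DXA is possible.** A reader might infer that a withdrawn participant can have no post-baseline DXA at all. Section 7.5 does not support that; week 12 is only the one scheduled scan.
- **Discretion in 7.5 may soften the rule.** It may, but 10.12 contains no exception and the two sections are not reconciled.
- **Exercise is part of the tested regimen.** True, so the thresholds are the sponsor's to set. That does not require stopping outcome measurement.

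It is also tempting to cite 11.2.2 as a precedent for efficacy follow-up. It is not one: it keeps people attending as a safety arm and mentions neither ITT nor an efficacy DXA. Nor is directional bias shown, because the same rule applies in both blinded arms.

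**Conclusion.** The point holds as an avoidable loss of primary-endpoint data. As worded, 10.12 removes randomized participants after two consecutive short weeks, and no clause brings them back for the only scheduled post-baseline DXA. That a single missed session makes a week short rests on whole-day scoring; the lack of retention does not.

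The size is unknown. It is probably small and within the planned 20% attrition. The larger figures require both lower adherence and little or no make-up of missed sessions, and both are assumptions. The stated sample size is correct. The reason to act is that the remedy costs almost nothing, not that the expected loss is large.

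**What to change.** State in protocol 10.12 that exercise non-compliance after randomization does not end follow-up: every consenting randomized participant attends the scheduled Visit 4 DXA and is analysed in ITT. A matching sentence in 7.5 would remove the conflict with its discretion wording.

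The cost is amendment text. The Visit 4 scan is already scheduled, so no visit or scan is added. The downside is that ITT will include some participants who exercised less than prescribed.

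Three clarifications are optional and for the sponsor to decide:

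- define the weekly score, including part-sessions;
- set the counselling and non-compliance tiers so that they can be told apart;
- add an exercise criterion to the PP definition (protocol 12.2, SAP 3), which now names product doses, major violations and completed visits and procedures. Participants withdrawn early generally fail the last condition today, so this matters mainly once they are retained.

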### **10.13 Laboratory Analyses**

12 hours fasting blood samples will be drawn from the participants at screening (Visit 1), baseline visit (Visit 2), and at the End of Study visit (Visit 4) as indicated in the schedule of assessments in Section 1.3.

Protection of subject confidentiality will extend to all data generated from the assaying of these samples. These samples will be alphanumerically coded and the persons performing the analysis will not be aware of the subject's identity or the product they received.

**At screening (Visit 1),** 18 mL of 12 hour fasting whole blood will be collected in:

1. Two 4 mL EDTA vacutainer tubes for:
  - a. CBC analysis (One tube)
  - b. HbA1c analysis (one tube)
2. Two 5 mL SST vacutainer tubes to generate serum for:
  - a. Na, K, Cl, Fe, Ca, Mg, phosphate, fasting glucose, TSH, Lipid Panel, creatinine, eGFR, BUN, GGT, ALP, AST, ALT, and total bilirubin analysis (one tube)
  - b. Fasting Insulin (One tube)

Protocol 20BWHM:

A randomized, double-blind, placebo-controlled study to investigate the effects of a *Bifidobacterium breve* strain on fat loss in healthy adults

3. Urine will be collected for urine pregnancy test of women of childbearing potential and urinalysis

**At baseline (Visit 2),** 18 mL of 12 hours fasting blood will be collected in:

1. Two 4 mL EDTA vacutainer tubes for:
  - a. CBC analysis (one tube)
  - b. Hb1-Ac analysis (one tube)
2. Two 5 mL SST vacutainer tubes to generate serum for:
  - a. Na, K, Cl, Fe, Ca, Mg, phosphate, fasting glucose, Lipid Panel, creatinine, eGFR, BUN, GGT, ALP, AST, ALT, and total bilirubin analysis (one tube)
  - b. Fasting Insulin (One tube)
3. Urine will be collected for urine pregnancy test of women of childbearing potential and urinalysis.
4. Fecal Sample also will be collected for analysis

**At the end of the study (Visit 4),** 18 ml of 12 hours fasting blood will be collected in:

1. Two 4 mL EDTA vacutainer tubes for:
  - a. CBC analysis (one tube)
  - b. Hb1-Ac analysis (one tube)
2. Two 5 mL SST vacutainer tubes to generate serum for:
  - a. Na, K, Cl, Fe, Ca, Mg, phosphate, fasting glucose, Lipid Panel, creatinine, eGFR, BUN, GGT, ALP, AST, ALT, and total bilirubin analysis (one tube)
  - b. Fasting Insulin (One tube)
3. Urine will be collected for urinalysis
4. Fecal Sample also will be collected for analysis

The total blood volume collection for the laboratory assessments listed above will be approximately 54 mL, over the period from screening to end of study. At any study visit, blood loss per volunteer is not expected to exceed 18 ml. Additional blood samples may be collected during the study in order to perform or repeat laboratory tests outlined in the Schedule of Assessments if needed.

Dynacare a central laboratory will be used in this study to measure blood parameters and urinalysis. Another lab will be used to process fecal samples.

Urine pregnancy test will be performed at the KGK Science clinic site.

Protocol 20BWHM:

A randomized, double-blind, placebo-controlled study to investigate the effects of a *Bifidobacterium breve* strain on fat loss in healthy adults

## **10.14 Termination of the Trial**

In the case of premature termination of the trial, participating investigators/participants, and the Institutional Review Board must be promptly informed of the termination. In the event of early termination, as many assessments will be completed as agreed upon by participant

## **10.15 Protocol Amendments**

If amendments to the study protocol are required after approval such changes will be captured in writing the reasons for the change documented and signed and dated by the sponsor. Any such amendments may be subject to IRB and Health Canada review/approval prior to implementation. Exception: if it becomes necessary to alter the protocol to eliminate an immediate hazard to participants, an amendment may be implemented prior to IRB approval. In this circumstance, the Investigator must notify IRB and Health Canada in writing within five (5) working days of the implementation.

# **11 SAFETY INSTRUCTIONS AND GUIDANCE**

## **11.1 Adverse Events and Laboratory Abnormalities**

### **11.1.1 Adverse Events**

An adverse event (AE) is any untoward medical occurrence in a clinical investigation participant who has been administered an investigational product and does not necessarily have a causal relationship with this treatment. An AE can be any unfavorable and unintended sign (including an abnormal laboratory finding), symptom, or disease temporally associated with the use of a product, whether or not it is considered related to that product. Pre-existing conditions that worsen during a study are to be reported as AEs.

During the study, participants should record any adverse effects in their diary. At each visit the participant will be asked, "Have you experienced any difficulties or problems since I saw you last?". Any adverse events (AEs) will be documented in the study record and will be classified according to the description, duration, intensity, frequency, and outcome. The qualified investigator will assess any AEs and decide causality.

Intensity of AEs will be graded on a three-point scale (mild, moderate, severe) and reported in detail in the study record.

Mild: Awareness of event but easily tolerated

Moderate: Discomfort enough to cause some interference with usual activity

Severe: Inability to carry out usual activity

The causality relationship of investigational product to the adverse event will be assessed by the qualified investigator as either:

Protocol 20BWHM: A randomized, double-blind, placebo-controlled study to investigate the effects of a *Bifidobacterium breve* strain on fat loss in healthy adults

Most probable: There is a reasonable relationship between the investigational product and AEs. The event responds to withdrawal of investigational product (dechallenge) and recurs with rechallenge when clinically feasible.

Probable: There is a reasonable relationship between the investigational product and AEs. The event responds to dechallenge when clinically feasible.

Possible: There is a reasonable relationship between the investigational product and AEs. Dechallenge information is lacking or unclear.

Unlikely: There is a temporal relationship to the investigational product administration but there is no reasonable causal relationship between the investigational product and the AEs.

Not related: There is no temporal relationship to investigational product administration or there is a reasonable causal relationship between non-investigational product, concurrent disease or circumstance and the AEs.

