Several studies have also demonstrated that *B. breve* may improve parameters associated with obesity. Supplementation with *B. breve* in obese mice was shown to reduce visceral fat gain and to lower serum cholesterol, glucose, and insulin compared to the control group (14). In a randomized, double-blind, placebo-controlled trial, healthy adults consuming a high-fat diet supplemented with a probiotic mix containing *B. breve* had reductions in body weight and fat mass after 4 weeks of supplementation (15). In another randomized placebo-controlled trial overweight adults were supplemented with *B. breve* for 12 weeks. Results from the study showed significantly lower fat mass along with improvements in liver function and inflammatory markers such as  $\gamma$ -glutamyl transpeptidase (GGT) and high-sensitivity C-reactive protein (CRP) compared to the placebo group (10, 11).

Despite the promising results of probiotics and reductions in body weight and fat mass, weight management is multifactorial and sustained weight loss often has a low success rate. In conjunction with dietary intervention, regular exercise has been proposed to improve body composition, intestinal microbiota diversity, and digestion (16, 17). However, prolonged exercise may disrupt the gastrointestinal tract and reduce the abundance of beneficial bacteria (17). To counteract this effect, the use of probiotics combined with exercise intervention has been proposed for effectively managing weight loss. The combination of aerobic exercise and administration of probiotics has been examined in several clinical trials and it was found that the combination was effective in improving body composition and inflammatory responses (18-20).

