## **11.3 Reporting of SAEs And Unexpected Adverse Reactions**

The qualified investigator will be responsible for classification of an AE as an SAE within 24 hours of notification. Causality should be signed off by the qualified investigator prior to reporting to ethics and regulatory bodies. Notification of any serious adverse events must be made in writing to the study sponsor. The IRB will be notified of all product related SAEs and unexpected adverse reactions. All blinded SAE's or unblinded-participant-on-active product SAE's will be reported to the Therapeutics Products Directorate (TPD) in an expedited manner.

Protocol 20BWHM:

A randomized, double-blind, placebo-controlled study to investigate the effects of a *Bifidobacterium breve* strain on fat loss in healthy adults

KGK Science must notify the TPD of all blinded or unblinded-participant-on-active product serious adverse events and reactions as follows:

If it is neither fatal or life threatening, within 15 calendar days after the day on which the sponsor becomes aware of the information; and

If it is fatal or life threatening, must be reported as soon as possible, but not later than seven (7) days after the day on which the sponsor becomes aware of the information.

Protocol 20BWHM:

A randomized, double-blind, placebo-controlled study to investigate the effects of a *Bifidobacterium breve* strain on fat loss in healthy adults

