### 6.2 Adverse Events

A descriptive analysis will be provided for pre-emergent and post-emergent AEs. AEs will be presented along with the system organ class, preferred term, and lower-level term. Furthermore, description, frequency, severity, and relationship to study product will be reported for each AE.

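### The second limb of the 'Not related' causality category does not exclude a product relationship, so an event with both a product cause and another cause can be coded 'Not related'

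*Protocol*

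**What the plan says.** Protocol 11.1.1 has the qualified investigator place each adverse event in one of five causality categories. Three rest on a reasonable relationship with the product and differ by what happened on stopping or restarting it:

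- 'Most probable' needs resolution on stopping and recurrence on restarting.
- 'Probable' reads: "Probable: There is a reasonable relationship between the investigational product and AEs. The event responds to dechallenge when clinically feasible".
- 'Possible' reads: "Possible: There is a reasonable relationship between the investigational product and AEs. Dechallenge information is lacking or unclear".

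None of the three asks whether another cause exists. 'Unlikely' is for events that fit in time but have no reasonable causal link to the product. The last category has two limbs. The first is "Not related: There is no temporal relationship to investigational product administration". The second, joined to it by 'or', is that "there is a reasonable causal relationship between non-investigational product, concurrent disease or circumstance and the AEs".

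The rating is used in two places. Protocol 11.3 states: "The IRB will be notified of all product related SAEs and unexpected adverse reactions". Protocol 12.3.2 and SAP 6.2 report causality event by event; in the SAP's words, "relationship to study product will be reported for each AE". Neither document says which of the five categories count as product related.

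**The concern.** A causality scale should give each event one place, or say which category wins when two apply. Here the two ends of the scale can both be true of the same event, because one end is defined by the product and the other by everything except the product. 'Unlikely', a weaker denial than 'Not related', does require that a reasonable product relationship be absent; the second limb of 'Not related' does not.

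At stake is whether a serious event that could reasonably be due to the product reaches the IRB, and whether the relationship shown for each event in the final report means the same thing from one event to the next.

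**Working it through.** No sample size, power or rate bears on this point, and the plan gives no figure to reproduce. The check is to write the five definitions in 11.1.1 as logical conditions and see which categories each kind of event meets.

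**Conditions.** T: the event fits in time. R: a reasonable relationship with the product (taken to imply T). A: a reasonable alternative cause. D: the result of stopping and, where done, restarting the product, with four states: resolved and recurred; resolved only; information lacking; did not resolve.

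**Number of profiles.** With R present: 2 (A yes or no) x 4 (D) = 8. With R absent: 2 (T) x 2 (A) = 4. Total 8 + 4 = 12.

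| Product (R) | Alternative (A) | Dechallenge (D) or timing (T) | Categories met as written |
|---|---|---|---|
| yes | yes | resolved and recurred | Most probable, Probable, **Not related** |
| yes | yes | resolved | Probable, **Not related** |
| yes | yes | lacking | Possible, **Not related** |
| yes | yes | did not resolve | **Not related** only |
| yes | no | resolved and recurred | Most probable, Probable |
| yes | no | resolved | Probable |
| yes | no | lacking | Possible |
| yes | no | did not resolve | none |
| no | yes | fits in time | Unlikely, Not related |
| no | no | fits in time | Unlikely |
| no | yes | no fit in time | Not related |
| no | no | no fit in time | Not related |

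**Result as written.** All 4 profiles with both causes meet 'Not related'. Three of them also meet a related category; the fourth has nowhere else to go.

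**Effect of adding only the missing condition.** If the alternative-cause limb also requires that no reasonable product relationship exist, the 4 of 12 becomes 0 of 12. But the two-cause event that did not resolve on stopping then meets no category, because 'Possible' requires dechallenge information to be lacking or unclear and 'Probable' requires a response. Profiles with no category rise from 1 to 2. The added clause is therefore not enough alone.

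**Effect of also widening 'Possible'** to any event with a reasonable product relationship that does not meet 'Probable': profiles with no category fall to 0 of 12. Two overlaps remain, 'Most probable' with 'Probable' and 'Unlikely' with 'Not related'. Neither crosses the line between related and unrelated.

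**Where the rating matters.** In 11.3 the written notice to the sponsor covers any serious event, and expedited reporting to the regulator covers all blinded serious events. Neither depends on causality. Only the IRB sentence does. In 12.3.2 events are tabulated by category and treatment and their incidence is compared between arms, again without a causality filter.

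**The case against.** The best defence is that a clinician asked to rate the product's relationship to an event will read 'Not related' as meaning due to something else instead of the product, and will code a two-cause event 'Possible'. That reading is natural, and the text allows it equally. In three of the four two-cause profiles the wording permits 'Not related' without forcing it. But the protocol does not state that reading, and in the fourth profile it is unavailable. Blinding should prevent knowingly different coding between arms; it does not settle how a two-cause event is coded.

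A reader might infer several stronger things that the documents do not support:

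- *That such events drop out of the safety analysis.* They do not. SAP 6.2 and protocol 12.3.2 list every event whatever its causality. Neither names a count of related events, so an understated count is not a planned output; only a tabulation by relationship, if one were made, would be affected.
- *That serious events could go unreported altogether.* Sponsor and regulator reporting do not depend on the rating, and protocol 14.1 also binds the site to the IRB's own requirements, which may include local safety reporting.
- *That competing causes are built into the design because everyone exercises.* The introduction says that "prolonged exercise may disrupt the gastrointestinal tract and reduce the abundance of beneficial bacteria", but it speaks of prolonged exercise. The trial assigns 20 minutes at moderate intensity on 3 days a week, and Appendix III allows bouts of 5 to 10 minutes. Of the 3 x 16 = 48 assigned sessions, 3 x 4 = 12 fall in the run-in, when everyone takes placebo. Assigned exercise does not by itself make a reasonable causal relationship.
- *That the bias can be sized by arm.* The documents give no event counts from which to do so.

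**Conclusion.** The definitions overlap as a matter of wording: an event that is reasonably due to the product can be coded 'Not related' whenever another cause is also reasonable, and in one profile it can be coded nothing else. This is a stated rule with a missing condition, not an omitted detail.

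The consequence is narrow. It reaches IRB notification of serious events and the relationship reported for each event. It probably also reaches IRB notification of unexpected adverse reactions; that rests on taking 'reaction' in 11.1.3 to imply a link to the product, which the protocol does not spell out. Overall event incidence, sponsor and regulator reporting, the efficacy analysis and the sample size are untouched.

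The 4 of 12 describes the scale, not how often the problem will occur; that cannot be estimated from the documents. The count assumes that a reasonable product relationship implies a fit in time and that 'or' in 'Not related' is read literally. The point is worth correcting because an ethics-notification rule depends on the rating and the repair is small.

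**What to change.** In protocol 11.1.1:

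1. Add to the second limb of 'Not related': *and there is no reasonable relationship to the investigational product*.
2. State that an event with a reasonable product relationship is coded at least 'Possible' even when another cause is also reasonable.
3. Widen 'Possible' to cover every event with a reasonable product relationship that does not meet 'Probable', including one that did not resolve on stopping the product.

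In protocol 11.3 and SAP 6.2, define *product related* as Possible, Probable or Most probable.

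The cost is a few sentences across the two documents, with no change to visits, procedures or sample size. The downside is that somewhat more events in both arms will be coded as related, including some whose true cause lies elsewhere.
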